9.0 Data and Statistical Analysis

9.1 Hypotheses

The null hypotheses is that there is no difference in efficacy between topical sirolimus 2% and placebo ointment in improving the clinical severity/function/pain scores of the plantar lesions in EBS. The alternative hypothesis is that topical sirolimus 2% is superior to placebo ointment.

9.2 Sample size calculation

Recruitment of **8 subjects** needed to detect an average 30% improvement of foot function score between topical sirolimus 2% and placebo with standard deviation of 40%, with power >0.8 and two-sided significance level of 5% (Stanford Statistician Group, USA).

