5.0 Criteria for Subject Eligibility

5.1 Number of Participants

We aim to enroll a total of 8-10 patients in this study at Stanford University.

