6.0 Study Design and Intervention

6.1 Study Design

This study is a prospective, double-blind, randomized, placebo-controlled crossover study at Stanford University School of Medicine, USA. It includes a 6-week screening period, followed by a 4 Phase Pilot Clinical Trial (see Table 2).

Screening: Up to 6 weeks

Phase 1: 12-week treatment period

Phase 2: 4-week wash-out period

Phase 3: 12-week treatment period

Phase 4: 4-week wash out period

Follow-up: 8 weeks after end-of-trial visit.

This research study is expected to take approximately 40 weeks. There will be 2 different parts of the study which the subject may receive for initial treatment period either (a) placebo (no drug) or (b) study drug for 12 weeks, during their enrollment in the 40-week study. After the initial 12-week period, there will be a washout period consisting of 4 weeks, before starting secondary treatment. During the secondary treatment period, a switch will occur and subject will receive either the (a) placebo (no drug) or (b) study drug depending on which treatment was received initially. At some time point during the 40-week study, at least both feet will receive study drug. There will also be a post-treatment visit at week 16 and week 32, with a post study phone call at Week 40. The end of treatment period will occur at Week 12 and Week 28, with the final in-person study visit occurring at week 32. Structured phone calls made by a physician will occur at Week 2, Week 14, Week 18, and Week 40.

The EBDASI feet score needs to be within 20% of baseline to progress to Phase 3. If subject's score does not meet this criteria the Phase 2 wash-out can be extended to 6 weeks.

Treatments are switched after Phase 2.

In-person study visits:

- Week 0 (screening/baseline)
- Week 4
- Week 12
- Week 16
- Week 20
- Week 28
- Week 32

Structured physician phone-call will be scheduled at:

- Week 2
- Week 14
- Week 18
- Week 40

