6.4 Screening/Baseline Period

Before any study-specific interventions are performed, the appropriate written informed consent must be obtained for the trial and a separate consent for skin biopsy, which is an optional additional procedure.

To assess subject eligibility, all screening assessments as follows should be completed: eligibility criteria, medical history and physical exam, weight and height, demography, vital signs, concomitant medications, Epidermolysis Bullosa Diseases Activity Score (EBDASI), Quality of Life in Epidermolysis Bullosa (QOLEB), collection of blood for: metabolic panel, complete blood cell count with differential, urinalysis, lipid profile.

The participant will also be initiated in how to use the Fitbit and completion of daily diaries and the various different questionnaires to be used in the trial.

6.5 Treatment Period – Phase 1

Participants who meet all eligibility criteria will be randomized 1:1 to receive either topical sirolimus 2% or placebo ointment. The on-site Registered Nurse will teach the participant how to apply the ointment to both feet and will administer the first dose of IMP at week 0. Subsequent twice daily application of IMP to both feet will be performed by the participant, this will continue for 12 weeks.

6.6 Wash-Out Period – Phase 2

After completion of Phase 1 the participant will stop applying the IMP to the feet for a period of 4 weeks at which point their baseline activity will be assessed. If their EBDASI feet score is within 20% of baseline they can proceed to Phase 3.

6.7 Treatment Period – Phase 3

Participants who received topical sirolimus 2% during phase 1 will switch to placebo ointment and vice versa. Twice daily application of IMP will be continued by the participant for a further 12 weeks. The trial will remain double-blinded throughout.

6.8 Wash-Out Period – Phase 4

After completion of Phase 3 participants will enter a further 4-week wash-out period where they will stop applying the IMP to their feet. At the end of Phase 4 they will attend for their final end-of-trial physician visit.

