8.6 Efficacy Assessments

Clinical assessments of the extent and severity of plantar lesions will be performed throughout the study.

Foot Health Status Questionnaire (FHSQ)

The purpose of this questionnaire is primarily to measure foot health related to foot function and quality of life. There are 19 questions regarding foot health and its impact with 4 subscales: foot pain, foot function, footwear and foot health. It has been shown to have excellent validity and ability to detect change in clinical trials and has demonstrated good reliability (Riskowski et al., 2011).

Epidermolysis Bullosa Disease Activity Score (EBDASI)

The EBDASI is a validated scoring system that objectively quantifies the severity of EB affecting the entire body. It has been designed to evaluate the response to new therapies for the treatment of EB. It was developed and validated many times over in the literature (Loh et al., 2014)

EBDASI feet score

Is a subsection of the EBDASI and objectively quantifies activity and damage levels relating to the feet only. Activity is graded according to size and number of lesions (blisters/erosions) in specific anatomical area. Damage is graded according to the presence/absence of the following signs: erythema, pigmentation, poikiloderma, atrophy, hyperkeratosis, scarring and milia.

Method of defect assessment

Tracing of affected wounds will be performed using Visitrak Digital Wound Assessment System. This is a portable device that provides accurate, reproducible data for tracking wound progress (See Figure 2).

Quality of life in Epidermolysis Bullosa (QOLEB)

QOLEB is a Quality of Life Questionnaire specifically designed for people with EB. The QOLEB can be used to identify everyday life occurrences negatively affected by EB. It assesses change in quality of life over time, an important measure when assessing the success of new treatments for EB (Frew et al., 2009).

Plantar Pressure Measurements

The Podotech Elftman foot pressure scanner uses 1600 electronic sensors incorporated into a thin mat to measure pressures at various points on the soles of the feet. This analysis can be performed while standing to get a static analysis or when walking to get a dynamic analysis. Peak pressures can be calculated and can correlate with areas of hyperkeratosis and changes in loading due to pain. A before and after assessment of participants feet using this device will give us insight into how hyperkeratosis has changed as well as

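### Section 9.2: eight patients give about 45% power for a 30% difference with SD 40%, not the stated >80%, unless an unstated within-patient correlation of about 0.79 is assumed

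*Combined protocol and SAP*

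**What the plan says.** Section 9.2 is the only justification of the sample size. It says that 8 subjects are needed to detect an "average 30% improvement of foot function score between topical sirolimus 2% and placebo with standard deviation of 40%, with power >0.8", with a two-sided test at 5%. It names no test and no within-patient correlation, makes no allowance for dropout, and does not say whether the 40% describes the treatment difference within a patient or the score under one treatment.

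The other relevant statements are:

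- **Enrolment** (section 5.1): "We aim to enroll a total of 8-10 patients in this study at Stanford University". This is the total, not the number per sequence.
- **Design** (section 6.1): "This study is a prospective, double-blind, randomized, placebo-controlled crossover study". Each patient therefore serves as their own control over two 12-week periods. The same section also calls the study a pilot.
- **Unit of treatment** (section 6.5): "Subsequent twice daily application of IMP to both feet will be performed by the participant". Both feet get the same product in a given period.
- **Primary efficacy outcome** (sections 8.3 and 8.6): change in foot function on the FHSQ, a patient questionnaire: "There are 19 questions regarding foot health and its impact with 4 subscales".
- **Analysis** (section 9.3): the sirolimus–placebo comparison is named, but no model, unit of analysis or confidence interval.

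**The concern.** An effect of three quarters of a standard deviation is not normally detectable with 80% power in 8 paired observations, so the stated figure looked about a factor of two out in sample size.

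This matters because section 9.1 sets up a superiority hypothesis and section 9.2 tells the reader that the trial is adequately powered to test it. A reader who trusts power above 0.8 may take a non-significant result as meaningful evidence against the drug. If the power is really below one half, that result is uninformative.

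**Working it through.** **Inputs.** Difference δ = 30%, SD = 40%, two-sided α = 0.05 and n = 8 (all section 9.2); n = 8 to 10 in total (section 5.1); two-period crossover (section 6.1).

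**Formula.** For a paired t-test, the noncentrality is δ/(SD/√n) with n − 1 degrees of freedom. Power is the probability that a noncentral t variable exceeds the two-sided 5% critical value in absolute size. A period term leaves n − 2 degrees of freedom.

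**Step 1: try to reproduce the stated figure, with 40% as the SD of the within-patient difference.** At n = 8 the noncentrality is 30/(40/√8) = 2.12, which is below the critical value of 2.36 on 7 degrees of freedom. Power must therefore be under one half.

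| Patients | Power, paired t | Power with period term |
|---|---|---|
| 8 | 0.449 | 0.430 |
| 9 | 0.507 | 0.492 |
| 10 | 0.562 | 0.549 |
| 16 | 0.8006 | 0.797 |

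A simulation at n = 8 gave 0.450. The smallest n for 80% power is 16, or 17 with a period term. The normal approximation, ((1.960 + 0.842) × 40/30)² = 13.96, gives 14.

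**Step 2: other calculations at n = 8.**

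| Variant | Power |
|---|---|
| Normal approximation, two-sided | 0.564 |
| Paired t, one-sided 5% | 0.605 |
| Normal approximation, one-sided 5% | 0.683 |
| Two independent groups, 4 v 4 (t) | 0.147 |
| Two independent groups, 8 v 8 (t) | 0.287 |

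None reaches 0.8. The one-sided rows also contradict the two-sided level that section 9.2 states.

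**Step 3: read 40% as the SD under each treatment.** The SD of the difference is then 40 × √(2(1 − ρ)), where ρ is the within-patient correlation. The documents give no ρ, so a range is shown.

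| ρ | SD of difference | Power, n = 8 | Power, n = 10 |
|---|---|---|---|
| 0 | 56.6% | 0.255 | 0.323 |
| 0.3 | 47.3% | 0.341 | 0.433 |
| 0.5 | 40.0% | 0.449 | 0.562 |
| 0.7 | 31.0% | 0.653 | 0.778 |
| 0.8 | 25.3% | 0.819 | 0.914 |

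Power of 0.80 requires an SD of the difference of at most 25.95% at n = 8, so ρ ≥ 1 − 25.95²/(2 × 40²) = 0.79. At n = 10 the limit is 30.12%, so ρ ≥ 0.72.

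**Step 4: a possible origin of the figure.** Sixteen paired units give 0.8006, which fits a claim of just over 0.8. Eight patients with two feet each, or 8 patients per sequence, would make 16. This is inference, and the error does not depend on it. Neither count is available: both feet share the treatment, the outcome is a patient's questionnaire response, and enrolment is 8–10 in total. Even if each foot had its own score with SD 40% for the difference, averaging the two feet gives an SD of 40 × √((1 + ICC)/2). Power with 8 patients is then 0.731 if the feet are unrelated and 0.559 at an intraclass correlation (ICC) of 0.5.

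**Step 5: what 8–10 patients can deliver with an SD of the difference of 40%.**

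- Difference detectable with 80% power: at n = 8, 30 × 40/25.95 = 46%; at n = 10, 30 × 40/30.12 = 40%.
- Expected 95% CI half-width, on the plan's percentage scale: at n = 8, 2.365 × 40/√8 = ±33; at n = 10, 2.262 × 40/√10 = ±29.
- Dropout, as an assumed range: 7 completers give power 0.386, and 6 give 0.321.

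**The case against.** The strongest objection is that section 9.2 does not define its SD. If 40% is the SD under each treatment, power at 8 patients runs from 0.26 to 0.82 as the correlation goes from 0 to 0.8, so 0.45 is one point in a range and the claim could be true. That is correct as far as it goes. But the sentence attaches the SD to the improvement between sirolimus and placebo, which most naturally means the difference. The rescue also needs a correlation of at least 0.79 that appears nowhere in the documents. On either reading, section 9.2 does not support its own figure.

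Two qualifications stand. First, a non-significant result is the likelier outcome at 8 patients, the number in section 9.2, but not at 10, where power is 0.56; at 9 it depends on whether a period term is fitted (0.507 without, 0.492 with). Second, no section says how a non-significant result would be interpreted, so the harm described is a risk and not a stated intention.

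It can also be said that this is a small pilot in a rare disease: section 6.1 uses the word, and section 6.2 counts only 24 people with a known KRT5/14 mutation in the recruitment databases. That is a good reason to accept 8–10 patients. It is not a reason to keep a power statement that is wrong, alongside a superiority hypothesis.

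**Conclusion.** The concern holds. With the plan's own inputs, and 40% taken as the SD of the within-patient difference, power is 0.45 with 8 patients (0.43 with a period term) and 0.56 with 10, against a stated value above 0.80. The sample that would match the claim is 16 patients, twice the number given. At 8 patients a true 30% effect would be missed about 55% of the time (1 − 0.449 = 0.551), and the expected confidence interval half-width of ±33 exceeds the 30% target itself.

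These results assume normally distributed differences, complete data and no carryover. The conclusion would change only if 40% is a per-treatment SD and the within-patient correlation is at least 0.79 at 8 patients (0.72 at 10), which the sponsor would have to state and justify. Because this is the sole basis for the sample size, it must be corrected.

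**What to change.** Keep 8–10 patients and replace the power statement in section 9.2 with wording such as:

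> *With 8 (10) patients and an SD of the within-patient treatment difference of 40%, a two-sided 5% paired t-test has about 45% (56%) power for a 30% difference. Power of 80% corresponds to a difference of 46% (40%). The trial is a pilot; the treatment effect will be reported with its 95% confidence interval, and a non-significant result will not be taken as evidence of no effect.*

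If 40% was meant as the SD under each treatment, say so, and give the correlation needed for 80% power (at least 0.79 with 8 patients, 0.72 with 10) and the evidence for it. In either case, name the test and say what the percentages are percentages of.

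In section 9.3, add that the unit of analysis is the patient and not the foot, and that the primary comparison is reported as an estimate with its 95% confidence interval.

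The cost is a few sentences in sections 9.2 and 9.3. No patients, visits, treatments or endpoints change. The price is a less favourable stated power.

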9.3 Treatment comparisons

The primary comparison of interest is between placebo and topical sirolimus 2% on foot function using the validated Foot Health Status Questionnaire.

Secondary comparisons of interest will be made between placebo and topical sirolimus 2% on the secondary outcome measures.

10.0 Study conduct considerations

10.1 Posting information on Clinical Trials Registers

Study information from this protocol will be posted on publicly available clinical trial registers before enrollment of participants begins. (clinicaltrials.gov)

10.2 Regulatory and ethical considerations

The study will be conducted in accordance with ICH Good Clinical Practice, and the ethical principles that are outlined in the Declaration of Helsinki 2008.

10.3 Records storage

Following closure of the study, the investigator will maintain all site study records in a safe and secure off-site location for duration of 15 years. The records will be easily accessible when needed and will be available for review by regulatory bodies.

All of the records will be maintained in a format other than hard copy (e.g. scanned, electronic).

10.5 Protected Health Information

During screening, patient's initials must be used for tracking purposes. If the subject enrolls in the study, then name and medical number will be necessary as each subject will have a medical chart during the study. Demographic information such as date of birth, phone numbers, and address will be used for communication purposes. Names and medical numbers will be required for lab and other necessary testing, clinic appointments, etc. This includes office visits for the study, medical history and medication history, blood test results, and processing of laboratory samples including tests. However, with exception of initials and subject number, no identifiers are included on survey instruments and questionnaires.

A complete list of health information and identifiers include:

Diagnosis and Procedures by visit
Clinical notes
List of ICD 9 diagnosis
Lab Test Results
Pathology reports
Radiology report
Pharmacy data/Medication list
Gender

Age at Diagnosis

MRN

Names

Contact information (phone number, address, email address)

Date of Birth

Medical History

10.6 Privacy and Confidentiality

Documents pertaining to the study and any other information received will be kept strictly confidential. The data may be reviewed by representatives of regulatory authorities only for the purpose of verifying procedures. Other than this, disclosure of data will only occur if it is required by law.

Physical documents will be kept within folders, which will be locked within the Department of Dermatology, St George Hospital. Electronic data will be kept on locked departmental computers and stored in password-protected files. Only study staff will have access. Records pertaining to the study will be kept for 15 years in a secure location away from the study site. After this amount of time has transpired the records will be disposed of securely.

No identifying information will be included in publications or presentations of the results without prior written consent from the participant.

10.7 Genomic Data Sharing Plan¹

The data that will be shared:

I will share phenotypic and genotypic data associated with the collected samples by depositing these data at Database of Genotypes and Phenotypes (dbGaP), which is an NIH-funded repository. Additional data documentation and de-identified data will be deposited for sharing along with phenotypic data, which includes demographics, family history of Epidermolysis bullosa simplex disease, and diagnosis, consistent with applicable laws and regulations. I will comply with the NIH GWAS Policy and the funding Institute and Centers existing policies on sharing data on Epidermolysis bullosa simplex disease genetics to include secondary analysis of data resulting from a genome wide association study through the repository. Meta-analysis data and associated phenotypic data, along with data content, format, and organization, will be available at Database of Genotypes and Phenotypes (dbGaP). Submitted data will conform to relevant data and terminology standards.

Who will have access to the data:

I agree that data will be deposited and made available through Database of Genotypes and Phenotypes (dbGaP), which is an NIH-funded repository, and that these data will be shared with investigators working under an institution with a Federal Wide Assurance (FWA) and could be used for secondary study purposes. I agree that the names and Institutions of persons either given or

denied access to the data, and the bases for such decisions will be summarized in the annual progress report. Meta-analysis data and associated phenotypic data, along with data content, format, and organization, will be made available to investigators through Database of Genotypes and Phenotypes (dbGaP).

Where will the data be available:

I agree to deposit and maintain the phenotypic data, and secondary analysis of data (if any) at Database of Genotypes and Phenotypes (dbGaP), which is an NIH-funded repository. The repository has data access policies and procedures consistent with NIH data sharing policies.

When will the data be shared:

I agree to deposit genetic outcome data into Database of Genotypes and Phenotypes (dbGaP) repository as soon as possible but no later than within one year of the completion of the funded project period for the parent award or upon acceptance of the data for publication, or public disclosure of a submitted patent application, whichever is earlier.

How will researchers locate and access the data:

I agree that I will identify where the data will be available and how to access the data in any publications and presentations that I author or co-author about these data, as well as acknowledge the repository and funding source in any publications and presentations. As I will be using Database of Genotypes and Phenotypes (dbGaP), which is an NIH-funded repository, this repository has policies and procedures in place that will provide data access to qualified researchers, fully consistent with NIH data sharing policies and applicable laws and regulations

NOTE: NIH is currently updating their guidance on data sharing plans, which will be available soon. For questions, contact the NIH Office of Extramural Research (OER) at [contact] or your RPM.

12.0 Tables

Table 1: Review of topical sirolimus use in dermatological disease (Fogel et al., 2015)

Indication	No. of patients	Vehicle	Concentration	Frequency	Duration, wk	Improvement	Irritation*	Serum levels	Study	Year
Chronic erosive oral lichen planus	7	Solution	0.1%	BID	12	Yes	Yes	Undetected/ <1.5 ng/mL	Soria et al ⁵⁴	2009
Familial multiple discoid fibromas	1	Solution	0.1%	BID	16	Yes	Yes	Undetected	Wee et al ⁵⁷	2013
Pemphigus vulgaris (mucosal lesions only)	3	Mouthwash	0.1%	BID	2-3	No	No	NA	Poot and Jonkman ⁵⁸	2012
Tuberous sclerosis facial angiofibromas	1	Ointment	1%	BID	12	Yes	No	Undetected	Haemel et al ⁵⁹	2010
	1	Ointment	1%	BID	4	Yes	No	NA	DeKlotz et al ⁶⁰	2011
	2	Solution	0.10%	QID/BID	10-23	Yes	Yes	Undetected	Mutizwa et al ⁶¹	2011
	9	Ointment	0.20%	BID	12	Yes	No	Undetected	Wataya-Kaneda et al ⁶²	2011
	4	Solution/ ointment	0.10%	BID	24	Yes	Yes	NA	Foster et al ⁵	2012
	2	Cream ± oral rapamycin	0.10%	QID	12-24	Yes	No	NA	Kaufman McNamara et al ⁶³	2012
	23	Cream	0.003%-0.015%	QID	24	Yes	2/23 Patients	Undetected	Koenig et al ⁶⁴	2012
	10	Ointment	0.40%	3 Times/wk	36	Yes	No	<0.3 ng/mL	Salido et al ⁶⁵	2012
	1	Cream	1%	QID	6	Yes	No	<0.3 ng/mL	Truchuelo et al ⁶⁶	2012
	2	Ointment	0.20%	BID	12	Yes	No	<0.3 ng/mL	Wataya-Kaneda et al ⁶⁷	2012
11	Ointment/gel	0.20%	BID	12	Yes	No	Undetected	Tanaka et al ⁶⁸	2013	
2	Cream	0.10%	QID/BID	52	Yes	No	Undetected	Wheless et al ⁵⁵	2013	
19	Ointment	0.1%-1%	BID-3 times/wk	32-120	Yes	No	Undetected (17/19), 5 µg/L (1/19), 8 µg/L (1/19)	Tu et al ⁶⁹	2014	

BID, Twice daily; NA, not applicable; QID, once daily; QID, four times daily; Wk, week.
*Irritation was the only reported side effect in all reports.

Schedule of Events:

Study period	Phase 1 ^b Screening/Baseline	Phase 1 ^b	Phase 1 ^b	Phase 1 ^b	Phase 2 ^c	Phase 3 ^d	Phase 3 ^d	Phase 3 ^d	Phase 3 ^d	Phase 4 ^e	Follow-up ^f
				(EOT) ^a	□ ^g WASH-OUT		□ ^g		(EOT) ^a		□ ^g
Visit Number	1	□ ^g	2	3		4	□ ^g	5	6	7	□ ^g
Study Week	Week 0	Week 2	Week 4	Week 12		Week 16	Week 18	Week 20	Week 28	Week 32	Week 40
Informed Consent/Assent (If applicable)	X										
Epidermolysis Bullosa Genotyping (Optional)	X										
Verify eligibility criteria	X										
Vital signs	X		X	X		X		X	X	X	
Medical history	X										
Adverse events	X	X	X	X	X	X	X	X	X	X	X
Serious Adverse events	X	X	X	X	X	X	X	X	X	X	X
Concomitant medications	X		X	X		X		X	X	X	
Mexameter erythema score	X		X	X		X		X	X	X	
Medical Exam	X			X					X		
Foot Health Status Questionnaire	X		X	X		X		X	X	X	
Defect area measurement using Visitrak	X		X	X		X		X	X	X	
2D photography of feet	X		X	X		X		X	X	X	
EBDASI feet score	X		X	X		X		X	X	X	
EBDASI total score	X			X		X			X		
QOLEB	X			X		X			X		
5-D Pruritus Scale	X			X		X			X	X	
Plantar pressure measurement	X			X		X			X	X	
Study drug collection/weighing/accountability	X		X	X		X		X	X		
Supervise study drug self-administration ¹	X		X			X		X			
Fitbit (daily)	X	X	X	X	X	X		X	X	X	X

Collection of blood for:											
Urine Pregnancy Test ^h	X		X	X		X		X	X	X	
				(EOT) ^a					(EOT) ^a		
Visit Number	1	□ ^b	2	3	□ ^b WASH-OUT	4	□ ^b	5	6	7	□ ^b
Study Week	Week 0	Week 2	Week 4	Week 12		Week 16	Week 18	Week 20	Week 28	Week 32	Week 40
Sirolimus trough level			X	X				X	X	X**	
Urinalysis	X			X		X			X	X	
CBC	X		X	X		X		X	X	X	
Metabolic panel	X		X	X		X		X	X	X	
Lipid profile	X		X	X		X		X	X	X	
Skin biopsy (optional)	X			X		X			X		
Structured phone-call		X				X		X			X

If a washout period is needed prior to baseline, subject has up to 6 weeks before starting treatment.

a. EOT= End of Treatment

b. After screening, subject will be randomized and enter Phase 1, the initial treatment application period. Subject will receive study drug or vehicle during this 12-week treatment period.

c. When Phase 1 is complete, a wash-out period will occur, which will last 4 weeks.

d. Phase 3 is the secondary treatment application period. The subject will receive either study drug or vehicle, switching from treatment initially used in Phase 1 during this secondary 12-week treatment period. Phase 3 may be delayed if subject has not reached 20% baseline EBDASI activity / Visitrak 2cm diameter.

e. Phase 4 will be a 4 week follow-up period after study treatment has concluded.

f. A scheduled phone call will occur at Week 40, after post treatment period at Phase 3.

g. Structured physician phone-call will be scheduled

h. Eligible female subjects of childbearing potential

i. Application occurs at the site on visit days

Table 3: Trial Objectives and Outcome Measures

Primary Objectives	Primary Outcomes

1. To assess for efficacy of topical sirolimus to improve foot function in the majority of participants with EBS at the end of each treatment versus baseline.
 
2. Safety and tolerability of topical sirolimus 2% cream
	
Foot function utilizing the validated Foot Health Status Questionnaire (FHSQ) as a change from baseline to the end of each treatment.
 <hr/> 
Primary Outcomes
 
Recording of adverse events, serious adverse events. Evaluation of any systemic absorption of topical sirolimus 2% through measurement of sirolimus trough levels in serum. Additional laboratory tests including full blood count, lipid panel, urea and electrolytes and liver enzymes at baseline through to week 40 will be performed.

Secondary Objectives	Secondary Outcomes

3. To assess the efficacy of topical sirolimus to improve clinical severity of lesional skin, including pain and itch symptoms, in the majority of participants with EBS at the end of each treatment versus baseline.
	
a) Plantar defect size measurements using Visitrak and 2D photography (% change in total defect area) from baseline to the end of each treatment.
 
b) EB Disease Activity and Scarring Index (EBDASI) feet activity scores as a change from baseline to the end of each treatment
 
c) Quality of life assessment in EB (QOLEB) as a change from baseline to the end of each treatment.
 
d) Itch severity measured using 5-D Pruritus Scale as a change from baseline to the end of each treatment.
 
e) Participants will wear a FitBit® for the duration of the study to assess number of steps walked per day as a change from baseline to the end of each treatment.
 
f) Changes in peak foot pressures and loading, before and after treatment using the Podotech Elftman foot pressure scanner as a change from baseline to the end of each treatment.
 
g) An erythema score of the soles of the feet will be obtained through use of Mexameter® MX 18 to detect any change in erythema at each study visit. This will be an objective measure of local skin irritation at the treatment site.
 
h) Molecular biology study of skin biopsies assayed for mTOR pathway inhibition (e.g. determination of phosphoprotein inhibition included ribosomal protein S6, S6 kinase and/or eIF-4E binding protein) as a change from baseline to the end of each treatment.

Figure 1. Schematic of the proposed study

[figure not shown]
[figure not shown]

Figure 2. Method of defect measurement using Visitrak Digital Wound Assessment System

Tracing of affected areas (hyperkeratosis or wounds)

- A. Selection of paired chronic wounds in a patient with RDEB.
- B. Wound size measurements made by 2-D tracing method.
- C. RDEB wound ulcers improved after vehicle injections at baseline, with a maximum response at 3 months (Venugopal et al., JAAD 2013). The same visitrak method will be used to trace affected areas in EBS.
